9 CLINICAL MONITORING

As a sponsor for clinical trials, FDA regulations require the CCR to maintain a monitoring program. The CCR's program allows for confirmation of: study data, specifically data that could affect the interpretation of primary and secondary study endpoints; adherence to the protocol, regulations, ICH E6, and SOPs; and human subjects protection. This is done through independent verification of study data with source documentation focusing on:

- Informed consent process
- Eligibility confirmation
- Drug administration and accountability
- Adverse events monitoring
- Response assessment.

The monitoring program also extends to multi-site research when the CCR is the coordinating center.

This trial will be monitored by personnel employed by a CCR contractor. Monitors are qualified by training and experience to monitor the progress of clinical trials. Personnel monitoring this study will not be affiliated in any way with the trial conduct.

10 STATISTICAL CONSIDERATIONS

10.1 STUDY ENDPOINTS

- Primary Endpoint:
 - The primary endpoint of this study is to determine the overall response rate (ORR) in patients with multiple myeloma treated with avelumab and irradiation.
- Secondary Endpoints:
 - The secondary endpoints are to determine:
 - Complete Response (CR) rate and Minimal Residual Disease (MRD) negative CR rate,
 - Reductions in bone marrow (BM) and peripheral blood (PB) plasmacytosis,
 - Radiographic reduction in size, and/or FDG avidity (PET/CT) of extramedullary lesions,

- Radiographic reduction in size, and/or FDG avidity (PET/CT) of non-irradiated extramedullary lesions (abscopal effect)
- Progression-free survival (PFS)
- Overall survival (OS)
- All Grade, Grade 3-4, and serious adverse events, and
- ORR post cycle 1 (prior to XRT)
- Exploratory Endpoints
 - Correlative Studies may be performed in select patients where adequate samples are available:
 - Peripheral blood mononuclear cells (PBMCs):
 - Changes in 123 immune subsets including CD4 and CD8 T cells, natural killer [NK] cells, NK-T cells, regulatory T cells [Tregs], myeloid-derived suppressor cells [MDSCs], and dendritic cells and 114 refined subsets relating to maturation/function using multicolor flow cytometry
 - Changes in the function of select immune cell subsets (e.g. CD4 and CD8 effector T cells, NK cells, Tregs, and MDSCs)
 - Changes in tumor antigen specific T cells (e.g. brachyury, MUC1, and CEA) using intracellular cytokine staining for IFN γ , TNF, and IL2 and the degranulation marker CD107a
 - Changes in T-cell clonality score using adaptive biotechnologies TCRseq assay
 - Changes in inflammatory gene signature using Nanostring's nCounter Human PanCancer Immune Profiling Panel
 - Plasma/Serum:
 - Changes in sCD27, sCD40L
 - Changes in cytokines (IFN- γ , IL-10, IL-12, IL-2, IL-4, etc.), chemokines, antibodies, tumor-associated antigens, and/or other markers
 - Changes in VDJ copy number of MM clones
 - Bone Marrow:
 - Changes in immune subsets
 - Changes in VDJ copy number of MM clones
 - DNA genetic alterations and TMB of MM cells

10.2 STATISTICAL HYPOTHESIS AND SAMPLE SIZE DETERMINATION

Historically, anti-PD-1 monotherapy in MM has an overall response rate (PR+VGPR+CR+sCR) of approximately 5%. It would be desirable to demonstrate that the combination of avelumab and irradiation has a substantially higher response rate, of at least 10-15%. As such, this study will be conducted using a Simon minimax two-stage phase II trial design to rule out an unacceptably low ORR of 5% ($p_0=0.05$) in favor of an improved response rate of 20% ($p_1=0.20$). With $\alpha=0.05$ (probability of accepting a poor treatment=0.05) and $\beta=0.20$ (probability of rejecting a good treatment=0.20), the first stage will enroll 13 evaluable patients, and if 0 of the

13 have a clinical response, then no further patients will be accrued in this trial. If 1 or more of the first 13 patients have a response, then accrual would continue until a total of 27 evaluable patients have been treated. As it may take up to several months to determine if a patient has experienced a response, a temporary pause in the accrual may be necessary to ensure that enrollment to the second stage is warranted. If there are 1 to 3 patients with a response out of 27 patients, this would be an uninterestingly low response rate. If there were 4 or more of 27 (14.8%) who experienced a response, this would be sufficiently interesting to warrant further study in later trials. Under the null hypothesis (5% response rate), the probability of early termination is 51.3%.

It is expected that approximately 8-10 patients per year may enroll onto this trial. Thus, it is expected that 3 years may be required to enroll up to 27 evaluable patients. To allow for a small number of inevaluable patients and screen failures, the accrual ceiling will be set at 30 patients.

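### Is the trial under-powered because Section 10.2 calls a response rate of 10-15% desirable but sizes the study for 20%?

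*Combined protocol and SAP*

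**What the plan says.** All the relevant text is in one paragraph of the combined protocol and SAP, Section 10.2. It starts from history: "Historically, anti-PD-1 monotherapy in MM has an overall response rate (PR+VGPR+CR+sCR) of approximately 5" per cent. It then says it would be desirable to show a "substantially higher response rate, of at least 10-15" per cent. A connective presents the design as following from that aim, and the plan adopts a Simon minimax two-stage design to rule out 5% "in favor of an improved response rate of 20" per cent, with alpha 0.05 and beta 0.20.

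The rule is to stop if none of the first 13 evaluable patients responds, and otherwise to continue to 27. At the end, "If there are 1 to 3 patients with a response out of 27 patients, this would be an uninterestingly low response rate"; four or more of 27 (14.8%) would justify further study in later trials. The stated probability of early termination at 5% is 51.3%.

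Section 10.4.2 requires the response fraction to be reported with two-sided 90% and 95% confidence intervals.

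**The concern.** Read in sequence, the statements seem to disagree. The desirable rate is 10-15%, the alternative used for sizing is 20%, and an observed 11.1% is labelled uninteresting. A reader could conclude that the 80% power belongs to the 10-15% aim, when power there is much lower. If the regimen truly produced responses in 10-15% of patients, the trial would more often than not miss it at the lower end. A result of 3/27 or fewer might then be taken as evidence against activity that the plan itself calls worth having. The patients have exhausted, cannot have or cannot tolerate available therapy, so wrongly dropping a modestly active combination would matter.

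**Working it through.** **Inputs (Section 10.2).** p0 = 0.05, p1 = 0.20, alpha = 0.05, beta = 0.20; n1 = 13 with a stop at 0 responses; n = 27, so 14 patients in stage 2; success at 4 or more.

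**Formulas.** With X1 ~ Bin(13, p) and X2 ~ Bin(14, p):

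- P(early stop) = (1 − p)^13
- P(success) = Σ over x = 1, 2, 3 of P(X1 = x)·P(X2 ≥ 4 − x), plus P(X1 ≥ 4)

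**Step 1: reproduce the plan's figures.**

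- At p = 0.05, P(early stop) = 0.95^13 = 0.5133, the plan's 51.3%.
- At p = 0.05, P(success) = 0.3512×0.0301 + 0.1109×0.1530 + 0.0214×0.5123 + 0.0031 = 0.0416, within 0.05.
- At p = 0.20, P(success) = 0.1787×0.5519 + 0.2680×0.8021 + 0.2457×0.9560 + 0.2527 = 0.8011, so beta is 0.199, within 0.20.

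An exhaustive minimax search for these four inputs returns the same design: 13/27 patients, stop at 0, fail at 3 or fewer.

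**Step 2: the same rule between p0 and p1.**

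| True rate | Stop at stage 1 | Declared interesting |
|---|---|---|
| 5% | 51.3% | 4.2% |
| 10% | 25.4% | 27.1% |
| 15% | 12.1% | 57.5% |
| 20% | 5.5% | 80.1% |

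Power reaches 80% at a true rate of about 20.0%. If 10-15 is read as points gained over 5%, the range becomes 15-20% and power is 57.5% to 80.1%.

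**Step 3: is the cut-off of four sensible, given that 3/27 = 11.1%?** The intervals below are exact (Clopper-Pearson). The plan does not name an interval method, so exact is an assumption, and no two-stage adjustment is made.

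| Result | 90% interval | 95% interval |
|---|---|---|
| 3/27 | 3.1% to 26.3% | 2.4% to 29.2% |
| 4/27 | 5.2% to 30.8% | 4.2% to 33.7% |

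The lower 90% limit corresponds to a one-sided 5% test. Three responses do not exclude 5%; four do. If success were redefined as 3 or more of 27 with the same interim stop, the type I error at 5% would be 13.5%, well over the stated 5%.

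**Step 4: what would a design for 15% need?** A minimax design for 5% against 15% at the same error rates needs 52 evaluable patients (30 in stage 1; 6 or more responses for success). Section 10.2 expects 8 to 10 patients a year: 27/9 = 3 years as planned, against 52/9 ≈ 5.8 years.

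**The case for a change.** The strongest case is that the 10-15% sentence is the only justification offered for the design, and that no reading reconciles the whole paragraph. If 10-15% is meant as an observed threshold, 3/27 lies inside it and still fails. If it is meant as a gain over 5%, power at the lower end is only 57.5%. Moreover, no negative outcome excludes the desirable range. The exact 90% upper limits are 20.6% at 0/13, 16.4% at 1/27, 21.5% at 2/27 and 26.3% at 3/27, all above 15%. A flat label of uninteresting says more than the data could support.

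The arithmetic stands, and so does the observation that the sentence is loose. The inference that the plan is under-powered does not. It would need a claim of 80% power at 10-15%, and there is none: beta is stated directly beside p1 = 0.20. The aim is worded as a floor, which a 20% alternative satisfies. Lower power between the null and the alternative is a property of every such design and not a defect of this one. The fear that a negative result would be over-read is met largely by Section 10.4.2, because the intervals appear beside the response fraction and show directly what was not excluded.

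**Conclusion.** No change is needed. The Simon design is correctly calculated for 5% against 20%, and every figure the plan states for it is reproduced. Labelling 3/27 uninteresting follows from holding the type I error at 5%: an observed 11.1% is still compatible with a true 5%.

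The gap between 10-15% and 20% is a matter of wording. Any resolution of it that keeps the 20% alternative leaves the 13, the 27, both boundaries, the analysis and the reported estimates as they are. Sizing for 15% would nearly double the trial to 52 evaluable patients, which is a poor trade for a single-institution study titled a pilot and described in Section 10.4.3 as proof of principle. An analyst reporting three or fewer responses would sensibly say that 5% was not rejected and that 10-15% was not excluded, and the required intervals already support that statement.

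This rests on two assumptions: that exact intervals are used, and that the rule is applied to 27 evaluable patients as written.

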10.3 POPULATIONS FOR ANALYSES

Modified intention to treat: all patients who receive at least one dose of avelumab will be included in the statistical analyses performed.

10.3.1 Evaluable for toxicity:

All patients will be evaluable for toxicity from the time of their first treatment with avelumab.

10.3.2 Evaluable for objective response:

Only those patients who have measurable disease present at baseline and have received at least one dose of therapy will be considered evaluable for response.

10.4 STATISTICAL ANALYSES

10.4.1 General Approach

Response fractions, and time to event endpoints will be reported along with appropriate confidence intervals.

10.4.2 Analysis of the Primary Endpoints

The fraction of patients who experience a PR, VGPR, CR, or sCR using the study treatment will be determined by dividing the number of responders by the total evaluable patients. The fraction will be reported along with 90% and 95% two-sided confidence intervals

10.4.3 Analysis of the Secondary Endpoints

- CR rate: the fraction of patients who experience a CR or sCR using the study treatment will be determined by dividing the number of these responders by the total evaluable patients. The fraction will be reported along with 90% and 95% two-sided confidence intervals.
- MRDnegCR rate: the fraction of patients who experience an MRDnegCR using the study treatment will be determined by dividing the number of these responders by the total evaluable patients. The fraction will be reported along with 90% and 95% two-sided confidence intervals.
- Reduction of BM and PD plasmacytosis: Percent change in plasma cells in the PB and BM from baseline will be reported descriptively.

- Reduction of size, and/or FDG avidity of extramedullary lesions: Percent reduction of size, and/or FDG avidity, radiographically, of extramedullary lesions compared to baseline will be reported descriptively.
- PFS: will be determined using the Kaplan-Meier method, considering those who progress or die without progression as failures, and censoring those who do not.
- OS: will be determined using the Kaplan-Meier method.
- Safety and tolerability: overall tolerability in terms of adverse events will be evaluated with descriptive statistics to determine the safety of receiving avelumab in the context of irradiation in RRMM patients. NCI CTCAE v.5 will be used to grade adverse events.
- ORR post cycle 1: a milestone ORR at start of cycle 2 will be calculated as above to determine ORR of avelumab monotherapy after 1 cycle of therapy.

Each of these will be calculated starting from the date the patient enrolled onto the trial which corresponds to the date the patient signed the informed consent document. Appropriate confidence intervals will be reported for each of these measures. (Only PFS events occurring during the initiation and of the combination of irradiation and avelumab and after will be counted as this proof of principal study hypothesis is that the combination of BavXRT will be active.)

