2.2.2 Screening activities performed after a consent for screening has been signed

The following activities will be performed only after the subject has signed the study consent **or** the consent for study 01-C-0129 (provided the procedure is permitted on that study) on which screening activities will be performed. Assessments performed at outside facilities or on another NIH protocol within the timeframes below may also be used to determine eligibility once a patient has signed the consent.

NOTE: Assessments and procedures to confirm study eligibility should be completed within 28 days prior to registration (unless otherwise noted).

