6.3.4 Overall Survival

Overall survival (OS) is defined as the duration of time from the date of study enrollment until time of death. Patients without a death event will be censored at the date survival assessment was last evaluated (e.g., clinic visit, phone call).

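### Overall survival is timed from signed consent but analysed only in patients who receive avelumab, so the consent-to-dose interval counts as survival during which no analysed patient can die

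*Combined protocol and SAP*

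**What the plan says.** **Time zero.** Section 6.3.4 states: "Overall survival (OS) is defined as the duration of time from the date of study enrollment until time of death". The closing paragraph of section 10.4.3, which follows a list that includes OS and PFS, starts each of these measures from "the date the patient enrolled onto the trial which corresponds to the date the patient signed the informed consent document".

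**Who is analysed.** Section 10.3 defines one general set, a modified intention-to-treat population: "all patients who receive at least one dose of avelumab will be included in the statistical analyses performed". No separate population is named for OS.

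**Method.** Section 10.4.3 says "OS: will be determined using the Kaplan-Meier method", and section 6.3.4 says "Patients without a death event will be censored at the date survival assessment was last evaluated". Neither mentions delayed entry or a landmark.

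**What lies between consent and first dose.** Section 2.2.2 says of screening that "The following activities will be performed only after the subject has signed the study consent" or, as the alternative, "the consent for study 01-C-0129 (provided the procedure is permitted on that study) on which screening activities will be performed". Eligibility assessments "should be completed within 28 days prior to registration". Baseline work (section 2.4) and registration also precede treatment (section 3.5). Section 10.2 sets an accrual ceiling of 30 for 27 evaluable patients to allow for inevaluable patients and screen failures, and section 3.8.2 takes screen failures off study.

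**The concern.** The clock starts at one event (consent) and membership of the analysis set is decided by a later one (first dose). A consented patient who dies or deteriorates before dosing never enters the analysis. Everyone who does enter was alive at first dose, so the time before it is death-free by construction. Counting that time as survival is the usual immortal-time problem.

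The bias runs in one direction, and it depends on how long each patient takes to get from consent to treatment, not on the treatment. A single-arm OS curve is read mainly against outside series. Set beside a series timed from treatment start, this one would look better than it should.

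**Working it through.** **Figures in the plan.** The plan gives no OS target, median or benchmark to reproduce. Its one design figure concerns response rate. Under a 5% response rate the chance of stopping after 13 patients is 0.95^13 = 0.513, which matches the stated 51.3%. The full design (stop at 0 of 13, success at 4 or more of 27) gives a type I error of 0.0416 and power of 0.801 at a 20% rate. None of this uses the OS clock.

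**Inputs for OS.**
- From the documents: origin at consent (6.3.4, 10.4.3), entry at first dose (10.3), plain Kaplan-Meier (10.4.3).
- Assumed, because the documents give neither: the gap g from consent to first dose, and the median m of survival T from first dose, taken as exponential. One month is 30.4375 days.

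**Formula.** Reported survival time is g + T, and only patients alive at g are in the set. For a common gap:
- S_reported(t) = 1 for t ≤ g, and S_T(t − g) for t > g.
- The reported median is m + g.
- Reported 6-month OS is 2^(−(6 − g)/m), against 2^(−6/m) from first dose.

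**Results.**

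| Gap (assumed) | Shift in median | Median 6 mo reads | 6-mo OS (0.500 from dose) reads | Median 12 mo reads | 6-mo OS (0.707 from dose) reads |
|---|---|---|---|---|---|
| 3 days | 0.10 mo | 6.10 (+1.6%) | 0.506 | 12.10 (+0.8%) | 0.711 |
| 14 days | 0.46 mo | 6.46 (+7.7%) | 0.527 | 12.46 (+3.8%) | 0.726 |
| 28 days | 0.92 mo | 6.92 (+15.3%) | 0.556 | 12.92 (+7.7%) | 0.746 |

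Worked example for 28 days and m = 6: g = 28/30.4375 = 0.92; 2^(−(6 − 0.92)/6) = 2^(−0.847) = 0.556.

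**Gaps that differ between patients.** In a simulation of 27 patients with gaps uniform on 0 to 28 days (20,000 repeats), the mean sample median moved from 6.17 to 6.64 months for m = 6, and from 12.30 to 12.76 months for m = 12. The mean shift was about 0.46 to 0.47 month. The curve must then stay at 100% only up to the shortest gap among the analysed patients.

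**The case against.** **The 28 days are not a consent-to-dose interval.** This is correct. Section 2.2.2 limits how old eligibility tests may be at registration. A reader might infer that every patient spends 28 days in screening after consent, that the OS curve is flat for that long, or that a 15% inflation is to be expected. The documents support none of these. The same section allows screening under the 01-C-0129 consent and the use of results from outside facilities or other NIH protocols, so some patients may sign the study consent shortly before dosing. Equally, no section caps the interval, so 28 days is not an upper limit.

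**Enrollment may mean something later.** Section 2.2.4 places enrollment next to the start of therapy when timing the pregnancy test. But section 10.4.3 defines it explicitly as the consent date, so the objection does not remove the problem. It does show that the term needs reconciling.

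**Timing from enrollment is common practice.** It is coherent when all enrolled patients are analysed. The defect is its pairing with a dosed-only set.

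**No decision depends on OS.** This stands. OS is secondary and descriptive, and no OS test, threshold or historical comparison is planned. Sampling error is also larger than the shift. With an assumed 6-month median and all 27 patients dead, an approximate 95% interval is 6 × exp(±1.96/√27), or 4.1 to 8.7 months. That limits the importance of the bias. It does not justify keeping a one-directional error that is easily removed.

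**Conclusion.** The point holds as a minor one. Sections 6.3.4, 10.3 and 10.4.3 read together put a death-free interval into every analysed patient's OS time, and nothing elsewhere in the plan corrects it. Any positive gap biases the curve and median upward; this direction needs no assumption about the size of the gap or the median.

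The size rests wholly on assumption: about 0.1 to 0.9 month on the median for gaps of 3 to 28 days, and roughly half the upper figure if gaps are spread evenly over 0 to 28 days. The 6-month OS of 55.6% in place of 50% needs a fixed 28-day gap for everyone and an exponential 6-month median; it is an illustration, not a forecast.

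A reader might also infer that the trial's conclusion is compromised. It is not: the response-rate design and decision rule do not use this clock. PFS shares the same origin, but the separate rule that leaves out PFS events up to Cycle 2 Day 1 is a different matter and is not judged here.

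**What to change.** In sections 6.3.3 and 6.3.4, and in the sentence of section 10.4.3 that sets the start date, time both OS and PFS from the first avelumab dose. Keep the consent date for accrual counts only, and bring the use of the word enrollment in section 2.2.4 into line.

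Both endpoints must move together. If OS alone moved, a patient who died without progression after Cycle 2 Day 1 would have a PFS time of g + T and an OS time of T, so PFS would exceed OS by the whole gap.

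First dose matches the analysis set in 10.3 and the start of toxicity evaluation in 10.3.1, and it should already be on record because section 6.1.1 records adverse events from Study Day 1. Two alternatives are also coherent: keeping consent as time zero with delayed entry at first dose, or analysing all consented eligible patients. The second would need survival follow-up of consented eligible patients who are never dosed.

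The cost is a wording change in three sections, with no new data and no change to sample size or decision rule. Reported OS and PFS become slightly shorter, and any comparison with a series timed from enrollment needs a note on the difference in origin.

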10.4.4 Safety Analyses

Early stopping rules for toxicities will be put in place. Specifically, if within the first 6 patients, there are two Grade ≥ 3 toxicities, or if at any time after 6 patients have been treated, the cumulative fraction with Grade ≥ 3 toxicity is 33% or greater, then the trial will suspend accrual and will only reopen following review of the safety data and amendment to modify the treatment appropriately. Adverse events which are clinically insignificant or can be resolved with conservative measures (e.g. laxatives for constipation) or which are not at least possibly due to the experimental treatment will not be included in this early stopping strategy.

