1.2.6 PD-1/L1 inhibitors in MM

Despite the overwhelming success of monotherapy PD-1/L1 inhibitors in the treatment of solid tumors, their monotherapy activity is marginal and disappointing in MM. For example, in the phase 1b study of nivolumab treatment in various hematologic malignancies, the response rate in the MM cohort was a modest 4% compared to B and T cell lymphomas.[39] Interestingly, in that study, the one response which was observed occurred in a patient who had received palliative radiation. Combination regimens blocking the PD-1 pathway however, have generated initial excitement. In MM, tumor cells, pDCs, and MDSCs express PD-L1, while the microenvironment of the bone marrow including resident cytotoxic T, NK, and NK-T cells express PD-1.[40, 41] Preclinical studies have shown that inhibition of the PD-1/PD-L1 interaction inhibits accessory cell induced MM proliferation and survival while activating host T- and NK-cell anti-MM tumor responses which can be augmented by the addition of lenalidomide.[42] These preclinical data led to a series of single arm clinical studies with reported response rates of 33 to 76%.[41, 43, 44] Two important phase 3 randomized studies evaluated lenalidomide or pomalidomide, dex, and +/- pembrolizumab. Unfortunately, at an interim analysis, the PD-1 inhibitor containing arms were associated with a detriment in overall survival leading to placing the study on hold and release of an FDA statement including Kaplan-Meier graphs.[45] The reasons and mechanisms of action leading to this detriment with the combination is currently unknown, however, it is unlikely that combinations with IMiDs will move forward.

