Grade ≥ 3 treatment-related TEAEs were observed in 177 subjects (10.2%) in the pooled safety dataset. The most frequently reported (at least 3 subjects, 0.2%) Grade ≥ 3 treatment-related TEAEs were fatigue, lipase increased (17 subjects each; 1.0%), GGT increased, infusion related reaction (10 subjects; 0.6%), AST increased (8 subjects; 0.5%), pneumonitis (7 subjects; 0.4%), anemia, blood CPK increased (6 subjects each; 0.3%), diarrhea, asthenia (5 subjects each; 0.3%), autoimmune hepatitis, ALT increased, amylase increased, hyponatremia, hypophosphatemia (4 subjects each; 0.2%). Other Grade ≥ 3 treatment-related TEAEs that were observed in 3 subjects (0.2%) included lymphopenia, adrenal insufficiency, hypothyroidism, colitis, vomiting, autoimmune disorders, lymphocyte count decreased, transaminase increased, decreased appetite and hypokalemia. In the pooled safety dataset, overall, a total of 4 deaths (0.2%) were due to TEAEs related to study treatment. The causes of death included pneumonitis, hepatic failure, and respiratory distress.

In the pooled safety dataset (N=1738), a total of 247 patients (14.2%) experienced immune related adverse events (irAEs). The median time to first onset of an irAE was 11.7 weeks. The most frequent irAEs were thyroid disorders including hypothyroidism (5.2%), hyperthyroidism (0.4%) and thyroiditis (0.2%), immune-related rash (5.2%), immune-related colitis (1.5%),

immune-related pneumonitis (1.2%), immune-related hepatitis (0.9%), adrenal insufficiency (0.5%), and immune-related myositis (0.5%). In addition, irAEs reported in 0.1% of patients in the pooled safety dataset included: Type 1 diabetes mellitus, immune-related nephritis and renal dysfunction, pituitary disorder, uveitis, and Guillain-Barré syndrome. The majority of irAEs were Grade 1 or Grade 2 in severity, with 39 (2.2%) being of Grade ≥ 3 severity. Fatal outcome was reported in 1 (0.1%) patient with immune-related pneumonitis, and 2 (0.1%) patients with immune-related hepatitis.

Clinical efficacy as provided in the USPI for approved indications:

JAVELIN Merkel 200 trial

Efficacy Endpoints	Results (N=88)
Overall Response Rate (ORR)	
Overall response rate, (95% CI)	33.0% (23.3%, 43.8%)
Complete response (CR) rate, (95% CI)	11.4% (6.6%, 19.9%)
Partial response (PR) rate, (95% CI)	21.6% (13.5%, 31.7%)
Duration of Response (DOR)	
	N=29
Range in months	2.8 to 23.3+
Patients with DOR ≥ 6 months, n (%)	25 (86%)

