7.3 NCI CLINICAL DIRECTOR REPORTING

Problems expeditiously reported to the OHSRP in iRIS will also be reported to the NCI Clinical Director. A separate submission is not necessary as reports in iRIS will be available to the Clinical Director.

In addition to those reports, all deaths that occur within 30 days after receiving a research intervention should be reported via email to the Clinical Director unless they are due to progressive disease.

To report these deaths, please send an email describing the circumstances of the death to [name] at [contact] within one business day of learning of the death.

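### The safety rule in 10.4.4 pools all related Grade ≥3 toxicity, so no written rule pauses accrual after a treatment-related death until the pooled limit is met

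*Combined protocol and SAP*

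**What the plan says.** Section 10.4.4 (Safety Analyses) has two limbs. The first applies "if within the first 6 patients, there are two Grade ≥ 3 toxicities". The second, used later in the trial, works on a running proportion: once pooled Grade ≥3 "toxicity is 33% or greater, then the trial will suspend accrual and will only reopen following review of the safety data". Suspension follows from either limb, and reopening also depends on a treatment amendment. Clinically insignificant events and events that resolve with conservative measures are left out, as are those "which are not at least possibly due to the experimental treatment will not be included in this early stopping strategy". A related death fits none of these exclusions, so it is counted, but only as one Grade ≥3 event. There is no separate criterion for Grade 4 events, Grade 5 events or death.

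The other provisions on deaths and serious events concern reporting and review:

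- Section 7.3: "all deaths that occur within 30 days after receiving a research intervention should be reported via email to the Clinical Director". Deaths from progression are exempt.
- Section 8.3: serious adverse events go to the sponsor's safety office within 24 hours.
- Section 8.7: serious, unexpected suspected reactions are reported to FDA.
- Section 7.4.1: the team meets about weekly and the principal investigator reviews adverse events, but continuation decisions are tied to efficacy data.
- Section 10.4.6: the planned interim analysis concerns response only.

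On background risk, section 1.2.8 reports that with single-agent avelumab "a total of 4 deaths (0.2%) were due to TEAEs related to study treatment", among 1738 patients. Section 13.1.2 adds fatal myocarditis and fatal pancreatitis.

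**The concern.** A pooled Grade ≥3 rule is a common and legitimate choice for judging overall tolerability. It is a blunt instrument for rare fatal events, because the limit must be high enough to tolerate ordinary Grade 3 toxicity. A limit near one patient in three is then far too high to react to deaths. This trial gives a new combination to patients in a single arm, and its own background records fatal related events with the study drug. If a related death occurs, whether enrolment continues while the case is examined is left to discretion. The plan writes a rule for Grade ≥3 toxicity in general but none for the gravest form of it.

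**Working it through.** **Inputs.** The limits of two events in the first 6 patients and 33% thereafter are from 10.4.4. The 27 evaluable patients and the ceiling of 30, which also allows for inevaluable patients and screen failures, are from 10.2. Section 10.3.1 counts toxicity in every patient from the first avelumab dose, so the number treated can exceed 27. Section 1.2.8 gives 4 related deaths and 177 patients with related Grade ≥3 events among 1738 (177/1738 = 10.2%). Sections 6.4 and 10.4.3 specify CTCAE v5; that a fatal event is Grade 5 is a convention of that scale.

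**The plan's own figure.** The plan gives no operating characteristics for the safety rule. For the efficacy design it states a 51.3% probability of early termination at a 5% response rate. 0.95^13 = 0.5133, so this reproduces.

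**Step 1: boundary.** The most counted events that pass is 1 for n ≤ 6, and for n > 6 the largest x with x/n < 0.33. Using 1/3 instead of 0.33 gives the same values.

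| Treated patients | Most events without suspension |
|---|---|
| 6 | 1 |
| 10 | 3 |
| 13 | 4 |
| 27 | 8 (8/27 = 29.6%) |
| 30 | 9 (9/30 = 30.0%) |

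A ninth event at n=27 triggers the rule (9/27 = 33.3%). The path to 8 is possible: one event among patients 1 to 6, then one each at patients 7, 10, 13, 16, 19, 22 and 25. It requires that no other Grade ≥3 toxicity is counted.

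**Step 2: how often the rule acts.** A patient-by-patient recursion was run with one counted event per patient at probability p, stopping at the first crossing. The documents give no related-death rate for this combination, so the rates d below are assumptions. With deaths only, p = d. With non-fatal events added, p = d + 0.102, treating the two groups of patients as separate. A first-death trigger fires with probability 1 − (1 − d)^27.

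| Assumed d | Current rule, deaths only | Current rule, plus 10.2% non-fatal | First-death trigger |
|---|---|---|---|
| 5% | 3.5% | 28% | 75% |
| 10% | 13.0% | 45% | 94% |
| 20% | 43.9% | 77% | 99.8% |

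All figures are by patient 27. If the non-fatal events are instead taken as independent of the deaths, p = 1 − 0.90 × 0.898 = 0.192 at d = 10%, and 45% becomes 41%. With no deaths at all, p = 0.102 alone gives 13%, so part of the 45% is the rule reacting to non-fatal toxicity.

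**Step 3: price of a first-death trigger.** At the single-agent rate, 4/1738 = 0.23%:

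- n=27: 1 − (1 − 4/1738)^27 = 6.0%.
- n=30: 1 − (1 − 4/1738)^30 = 6.7%.
- The exact 95% interval for 4/1738 is 0.063% to 0.588%, which gives 1.7% to 14.7% at n=27.
- At an assumed 1%: 1 − 0.99^27 = 24%. At an assumed 2%: 1 − 0.98^27 = 42%.

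**The case against.** The strongest reply is that 8 of 27 is a corner case. That stands. With deaths as the only counted events, the chance of reaching exactly 8 without suspension is under 3% at every assumed rate from 5% to 30%, and other toxicity makes it smaller still. A reader might infer from the limit that the plan accepts such a death toll; it does not say so, and the number is only where the arithmetic of the rule ends. The first limb also counts toxicities rather than patients, so one fatal case with two qualifying toxicities could trigger it.

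Second, deaths would not go unseen. Weekly team meetings, 24-hour reporting with no waiver (8.4) and FDA reporting are all in place, and accrual is slow at 8 to 10 patients a year. The investigator, sponsor, IRB or FDA could halt the trial. This is true and lowers the severity, but none of these provisions requires a hold.

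Third, a reader might tie the gap to section 1.2.6, where "the PD-1 inhibitor containing arms were associated with a detriment in overall survival". The documents do not support a direct link. That was a comparative signal from randomised trials with lenalidomide or pomalidomide, drugs not given here. Its mechanism is described as unknown, and it is not attributed to treatment-related deaths. A limb based on attributed deaths in a single arm would not detect it. The fatal related events in 1.2.8 and 13.1.2 are the relevant background.

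Fourth, a reader might infer from 4/1738 that a first-death trigger would rarely fire by chance. That rate comes from single-agent avelumab in solid-tumour and Merkel cell cohorts. It does not establish how often a death would be called at least possibly related in relapsed or refractory myeloma with radiotherapy.

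**Conclusion.** The point holds as a cheap improvement; it does not show a contradiction or an error in the plan. Section 10.4.4 is the only written rule that suspends accrual for harm, and it does not distinguish a related death from a Grade 3 event. Its upper limit is 8 related deaths in 27 treated patients, or 9 in 30. The more useful measure is sensitivity: at an assumed 10% related-death rate it suspends by patient 27 about 13% of the time on deaths alone, and about 45% with a further 10.2% of patients having counted non-fatal events. The 10% is an assumption. The 10.2% is borrowed from the single-agent pool and may be high, because 10.4.4 would exclude some of those events.

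**What to change.** Add a third limb to 10.4.4, for example: *Accrual will also be suspended after any death judged at least possibly due to the experimental treatment, until the safety data have been reviewed. For this limb, review alone suffices to reopen accrual; an amendment is needed only if the review calls for one.* The second sentence matters because the present text makes reopening depend on a treatment amendment as well as a review, which may not be warranted after a single death. The limb governs accrual only and changes nothing for patients already on treatment.

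The text costs two sentences. The operating cost is the chance of at least one accrual pause, which is the range worked out in Step 3. The sponsor should state the possibly-related death rate it expects in this population, since the cost depends on it. The plan already allows for a pause between stages (10.2), so a short hold is manageable.
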